#### Randomisation for Phase 2 Intervention RCT

Randomisation will be carried out using an internal STATA routine (Chaimani et al. 2013) by an independent member of the University of Manchester Biostatistics Group who will be responsible for this, along with conveying the allocation to the RA in order for the intervention pack to be sent to participants. This method ensures the statistician carrying out the analyses (MH) remains masked to treatment allocation.

Eligible participants will be allocated at random (1:1) in blocks of size 4, 6 or 8 (chosen at random and in equal numbers) to either the immediate lymphatic self-massage intervention plus UC or UC alone plus the intervention from 3 months. Due to the known gender differences between women and men both in terms of CFS/ME and also Long COVID itself, we will stratify for gender within the randomisation. We will set up the randomisation so that should extra sites outside of Salford be required to achieve recruitment targets, we will ensure a balance between the two trial arms.

All Phase 2 participants will receive a letter thanking them for completing the Phase 1 survey and letting them know which group they have been allocated to. The letter will explain how RCTs work and the importance of follow-up data irrespective of which group participants are allocated to, and that all participants will receive the intervention described but at different times, and that they will be followed up for 6 months in total (at 3m and 6m) using the same survey measures they have already completed in the baseline survey. One additional tick sheet will be used to capture participants' use of the intervention which will be sent to the intervention participants at 3m and 6m and to the control – wait-list group at 6 m only.

The group randomised to receive the intervention will receive this immediately after randomisation along with this letter. The UC wait-list control group will be sent the intervention pack after submission of their 3m follow-up data. We will not tell patients when to stop using the intervention but will monitor its use in the two study arms over time.

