#### Intervention components

There are three components to this intervention:

- Lymphatic self-massage: The instructions for lymphatic self-massage technique will be available to those in the intervention arm in both leaflet and online and DVD format (this will be password protected to reduce risk of those in the UC arm accessing the information before the 3 months when they are eligible to receive the intervention after the waiting-list period has elapsed).
- 2. Gentle spinal mobility & breathing exercises: again, these instructions will be provided online and in a DVD format.

\*Sponsor's representative: [name], Managing Director of Research & Innovation Norther Care Alliance NHS Foundation Trust, [name] [contact]; email: [contact]

 Contrast bathing: Participants will be recommended to place alternating warm and cool packs placed on the upper spine for a total of 10 minutes, once a day to stimulate circulation, following the this process; COLD - 3 minutes, WARM - 1 minute, COLD - 1 minute, WARM - 1 minute, COLD - 1 minute, WARM - 3 minutes, so 10 Minutes total.

The hot water bottle and gel pack required, along with a long handled back massager will be sourced and supplied by the research team to ensure participants have access to suitable equipment. Gel packs are currently sourced for CFS/ME patients receiving lymphatic drainage in clinic. We have been advised that this constitutes general equipment so does not require specific approval by Northern Care Alliance NHS Foundation Trust's Medical Equipment Management team (personal communication Dr [name]) and that a safety evaluation will suffice.

Participants in addition to receiving the equipment required will also receive the contact details for our Patient Liaison Advisor (OM) in case they wish to check any of the techniques with her this can be carried out using encrypted Zoom, MS Teams or WhatsApp video conferencing features.

Participants will be informed of the potential side effect of nausea and headache.

The usual care (UC) participants will receive the same equipment and access to the intervention instructions after their 3m follow-up has been completed.

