#### Follow-ups

Survey data collected in Phase 1 will be treated as baseline or 0-month data. Table 1 shows the schedule for subsequent study assessments. The CFQ, SF-12 and EQ5D-5D will be completed by the patient online or via a paper form returned to the research office. The 3m follow-up allows us to see any changes between those receiving the intervention and those not. The 6-month (6m) follow-up enables us to see if any benefits observed at 3m are maintained beyond the intervention period, and to compare this between the two groups.

	0m (baseline)	3m	6m
CFQ	Х	Х	Х
SF-12	Х	Х	Х
EQ-5D-5L	Х	Х	Х
Intervention diary		X (intervention group only)	X
Qualitative interview		X	X

Table 1: Assessments and timescales for the feasibility study

Proposed Primary outcome measures: These will be the logistical findings arising from the feasibility study (i.e. related to the conduct of the trial)

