#### 8.5 Stopping rules

It is not anticipated that the study will be stopped prior to its intended end-date. However, the study will be halted if:

- New information comes to light which means that the aims of the study are futile.
- Safety issues come to light regarding the intervention.
- Resources to conduct the study are no longer available.

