Adverse events, including serious adverse reactions (SARS) to trial interventions will be reported to the Sponsor and recorded and reported within the CONSORT diagram.

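### Adverse events are to be recorded and reported, but no scheduled form asks either arm about them, so counts will probably be incomplete and arm comparisons open to unequal capture

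*Protocol*

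**What the plan says.** The protocol's only adverse-event provision is the closing sentence of section 10: adverse events, with serious adverse reactions among them, "will be reported to the Sponsor and recorded and reported within the CONSORT diagram". It gives no method of collection, no timing, no recall period and no arm.

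Two other places bear on safety. Section 7.1, Intervention components, states: "Participants will be informed of the potential side effect of nausea and headache". Section 8.5 lists, among the reasons for halting the study: "Safety issues come to light regarding the intervention".

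Data collection is fixed in section 7.1. Under Follow-ups, "Table 1 shows the schedule for subsequent study assessments"; its rows are CFQ, SF-12, EQ-5D-5L, an intervention diary and a qualitative interview. Under Randomisation, participants are told that they will be followed up at 3 and 6 months "using the same survey measures they have already completed in the baseline survey". One form is added, a tick sheet on use of the intervention. It goes to the intervention arm at 3 and 6 months and to the wait-list arm at 6 months only.

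**The concern.** The protocol promises adverse events as an output but schedules no question that would produce them. In a trial run by post, telephone and online form, nobody sees the participants, so an event that is neither asked about nor volunteered is not recorded.

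Two things are at stake. The first is completeness: a short list in the CONSORT diagram could mean few events or few reports, and the data could not tell these apart. The second is comparability. Nausea and headache may also occur without the intervention in people with persistent symptoms after COVID-19, so a count in the treated arm needs a control count obtained in the same way. The only randomised treated-versus-untreated period is 0 to 3 months, and once it has passed the missing information cannot be recovered.

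**Working it through.** **Step 1: possible sources of adverse-event data, by arm, 0 to 3 months.**

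| Source (protocol section) | Intervention | Wait-list | Asks about adverse events? |
|---|---|---|---|
| CFQ, SF-12, EQ-5D-5L (7.1, Table 1) | yes | yes | no; none is described as recording nausea or headache as events |
| Diary / tick sheet (7.1, Table 1 and Randomisation) | yes | no | no; it records use |
| Interviews at 3 months (7.1, Qualitative Interviews) | 10 people | none | not stated; they cover acceptability, adherence, barriers and drivers |
| Liaison adviser (7.1, Intervention components) | yes, details come with the kit | not before the kit arrives, after 3 months | no; offered for checking technique |
| Drop-out reasons (10) | where possible | where possible | only for those who leave |

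No row is a planned question on adverse events, and three of the five exist in one arm only. At 6 months both arms have the tick sheet and interviews, but by then both have been given the intervention.

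**Step 2: how incomplete could the count be?** The protocol states no event rate or reporting rate, so there is no figure to reproduce and everything below is illustration. The one input from the protocol is 100 participants allocated 1:1 (section 6), so n = 50 per arm. The assumed inputs are an event rate p and a volunteered share c.

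P(no report) = (1 − p × c)^50

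- p = 10%, c = 10%: 0.99^50 = 0.605
- p = 10%, c = 20%: 0.98^50 = 0.364 (5 people affected, 1 report expected)
- p = 10%, c = 30%: 0.97^50 = 0.218

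Varying the event rate at c = 20%: p = 5% gives 0.99^50 = 0.605, and p = 20% gives 0.96^50 = 0.130. With every event captured and p = 10%, the chance of recording at least one is 1 − 0.90^50 = 0.995.

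**Step 3: what would a zero mean?** If all 50 people were asked and none reported an event, the one-sided 95% upper limit would be 1 − 0.05^(1/50) = 5.8%, and the two-sided exact 95% upper limit 1 − 0.025^(1/50) = 7.1%. Zero unsolicited reports support neither limit, because the number of people effectively asked is unknown.

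**Step 4: unequal capture.** Apparent difference = p × (c in the intervention arm − c in the wait-list arm). With equal true rates of 20% and assumed capture of 60% and 20%, this is 0.20 × (0.60 − 0.20) = 8 percentage points where the truth is 0. At true rates of 10% and 30% it is 4 and 12 points. With equal capture it is 0.

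**Step 5: what the same question in both arms would give.** With full capture and 50 per arm, the 95% half-width for a risk difference is 1.96 × √(p1(1 − p1)/50 + p2(1 − p2)/50). For 10% against 5% this is 10 points; for 20% against 10% it is 14 points. That is descriptive precision only, but it is not distorted by unequal capture.

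**The case against.** The strongest counter-argument is that symptom data may be collected in both arms after all. The Phase 1 survey includes a symptom tick box, the Randomisation text says that follow-up repeats the baseline measures, and the timetable in section 7 says that the same online questionnaires are used at 3 and 6 months. This makes repetition of the tick box possible but not established. It sits with the demographic and COVID-19 history items, is absent from Table 1, and is not described as adverse-event collection. It would be too firm to say that nausea and headache are certainly never recorded.

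Other routes also exist: drop-out reasons, interviews that deliberately include people who do not start or who drop out, withdrawal by the study clinician, and the sponsor's standard monitoring. All Phase 2 candidates receive a co-ordinator's number before consent. Its stated purpose is questions about joining, but both arms would hold it. These routes are real but partial, and none asks everyone the same question.

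A reader might infer more than the protocol supports:

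- **That no comparison by arm is possible.** Reports can be tabulated by arm; the difficulty is bias.
- **That the halting rule has no information behind it.** It has partial information.
- **That the larger trial would inherit a wrong tolerability figure.** Section 10 lists the SD, attrition, recruitment per area and effect sizes as inputs to that trial. No tolerability figure is planned, and safety is neither an aim nor a listed outcome.
- **That the CONSORT diagram will be presented as evidence of safety.** The protocol does not say so.
- **That nausea and headache are established side effects.** The protocol calls them potential.

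Finally, the form of tabulation and the intervals are commonly left to the SAP, which is not at hand. That is fair. But an SAP can only tabulate what is collected, and which questions are asked at 3 and 6 months is fixed by the protocol's schedule.

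**Conclusion.** The point holds as a gap between what the protocol commits to report and what it schedules to collect. Followed as written, adverse-event counts are likely to be incomplete, and the 0 to 3 month comparison by arm would be open to unequal capture. The safety halting rule depends on the same partial reports.

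The size cannot be stated from the protocol. The 61% to 22% chance of no report rests on an assumed 10% event rate, an assumed 10% to 30% volunteered share and 50 participants in the arm; the 8-point spurious difference rests on assumed capture rates. Both show how the mechanism works and do not estimate what will happen in this trial. The primary feasibility outcomes, recruitment and retention, are not affected. This is an inexpensive improvement that should be made, because the untreated comparison period cannot be revisited.

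**What to change.** Add an adverse-event row to Table 1 at 3 and 6 months for both arms. Use identical wording and the same recall period in each arm: fixed yes/no items for nausea, headache and any other new or worse problem. Add one sentence to section 10 saying that these items, together with volunteered reports, are the source of the adverse-event counts, and that the 0 to 3 month counts will be reported descriptively by arm. If the Phase 1 symptom tick box is meant to be repeated at follow-up, say so in Table 1 and state whether it serves this purpose.

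The cost is a few items on forms that are already being sent, and a minor amendment. The drawback is a slightly longer form for people with fatigue.

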# **11** Dissemination of Results and Publication Policy

We will aim to have research outputs in the form of original research articles published in Open Access peer review journals and will seek to raise the profile of our work at conference presentations. All the study team will be invited to participate in the writing, reviewing and editing of papers and will conform to guidance issues by IJCME.

Results of the study will be disseminated by the Northern Care Alliance NHS Foundation Trust via their website: Https://www.reserchforthefutureorg, newsletters and social media. This will ensure that volunteers who have participated in this research have access to the study findings

